7.2.2. Graded Laboratory Values

The Gilead Grading Scale for Severity of Adverse Events and Laboratory Abnormalities will be used for assigning toxicity grades to laboratory results for analysis as Grade 0, Grade 1, Grade 2, Grade 3, or Grade 4. Grade 0 includes all values that do not meet the criteria for an abnormality of at least Grade 1. Some laboratory tests have criteria for both increased and decreased levels; analyses for each direction (i.e. increased, decreased) will be presented separately.

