### **9.5.4. Laboratory Evaluations**

Selected laboratory data will be summarized using only observed data. Absolute values and changes from baseline at all scheduled visits will be summarized. Graded laboratory abnormalities will be defined using the grading scheme in Grading of Laboratory Abnormalities provided in [Appendix 3](#).

Incidence of treatment-emergent laboratory abnormalities, defined as values that increase by at least one toxicity grade from baseline at any time post baseline up to and including the date of last dose of study drug plus 30 days, will be summarized by age group and overall. If baseline

data are missing, then any graded abnormality (i.e., at least a Grade 1) will be considered treatment emergent.

All laboratory abnormalities will be included in the listings of laboratory data.

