**Appendix 3. GSI Grading Scale for Severity of Adverse Events and Laboratory Abnormalities**

Antiviral Toxicity Grading Scale Version: 01 April 2015

HEMATOLOGY				
	Grade 1	Grade 2	Grade 3	Grade 4
Hemoglobin HIV POSITIVE Adult and Pediatric ≥ 57 Days	8.5 to 10.0 g/dL 85 to 100 g/L	7.5 to < 8.5 g/dL 75 to < 85 g/L	6.5 to < 7.5 g/dL 65 to < 75 g/L	< 6.5 g/dL < 65 g/L
HIV NEGATIVE Adult and Pediatric ≥ 57 Days	10.0 to 10.9 g/dL 100 to 109 g/L OR Any decrease from Baseline 2.5 to < 3.5 g/dL 25 to < 35 g/L	9.0 to < 10.0 g/dL 90 to < 100 g/L OR Any decrease from Baseline 3.5 to < 4.5 g/dL 35 to < 45 g/L	7.0 to < 9.0 g/dL 70 to < 90 g/L OR Any decrease from Baseline ≥ 4.5 g/dL ≥ 45 g/L	< 7.0 g/dL < 70 g/L
Infant, 36–56 Days (HIV POSITIVE OR NEGATIVE)	8.5 to 9.4 g/dL 85 to 94 g/L	7.0 to < 8.5 g/dL 70 to < 85 g/L	6.0 to < 7.0 g/dL 60 to < 70 g/L	< 6.0 g/dL < 60 g/L
Infant, 22–35 Days (HIV POSITIVE OR NEGATIVE)	9.5 to 10.5 g/dL 95 to 105 g/L	8.0 to < 9.5 g/dL 80 to < 95 g/L	7.0 to < 8.0 g/dL 70 to < 80 g/L	< 7.0 g/dL < 70 g/L
Infant, 1–21 Days (HIV POSITIVE OR NEGATIVE)	12.0 to 13.0 g/dL 120 to 130 g/L	10.0 to < 12.0 g/dL 100 to < 120 g/L	9.0 to < 10.0 g/dL 90 to < 100 g/L	< 9.0 g/dL < 90 g/L

HEMATOLOGY				
	Grade 1	Grade 2	Grade 3	Grade 4
Absolute Neutrophil Count (ANC) Adult and Pediatric, ≥ 7 Months#	1000 to 1300/mm  1.00 to 1.30 GI/L	750 to < 1000/mm  0.75 to < 1.00 GI/L	500 to < 750/mm  0.50 to < 0.75 GI/L	< 500/mm  < 0.50 GI/L
Absolute CD4+ Count HIV NEGATIVE ONLY Adult and Pediatric > 13 Years	300 to 400/mm  300 to 400/μL	200 to < 300/mm  200 to < 300/μL	100 to < 200/mm  100 to < 200/μL	< 100/mm  < 100/μL
Absolute Lymphocyte Count HIV NEGATIVE ONLY Adult and Pediatric > 13 Years	600 to 650/mm  0.60 to 0.65 GI/L	500 to < 600/mm  0.50 to < 0.60 GI/L	350 to < 500/mm  0.35 to < 0.50 GI/L	< 350/mm  < 0.35 GI/L
Platelets	100,000 to < 125,000/mm  100 to < 125 GI/L	50,000 to < 100,000/mm  50 to < 100 GI/L	25,000 to < 50,000/mm  25 to < 50 GI/L	< 25,000/mm  < 25 GI/L

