1.2. Study Design

This is an open-label, multi-cohort, two-part study evaluating the PK, safety, and efficacy of SOF + RBV in chronic HCV-infected pediatric subjects.

The study will enroll both treatment-naïve and treatment-experienced pediatric subjects, with up to 20 subjects allowed to be treatment experienced. Approximately 100 total subjects will be enrolled as follows:

- Approximately 50 adolescents aged 12 to < 18 years
- Approximately 50 children aged 3 to < 12 years

Subjects of 3 age groups will be enrolled in a sequential fashion: 12 to <18 years old, followed by 6 to <12 years old, and 3 to <6 years old.

Eligible subjects will receive the following regimen based on HCV genotypes:

- Genotype 2 subjects: SOF + RBV for 12 weeks
- Genotype 3 subjects: SOF + RBV for 24 weeks

Therefore, subjects are grouped into the treatment groups specified in [Table 3-1](#) according to their age groups and HCV genotypes.

The schedules of assessments for the study are provided as appendixes to the SAP (see Study Procedures Table, [Appendix 1](#)).

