7.2. Laboratory Evaluations

Laboratory data collected during the study will be analyzed and summarized using both quantitative and qualitative methods. Summaries of laboratory data will be provided for the Safety Analysis Set and will include data collected up to the last dose of study drug plus 30 days for subjects who have permanently discontinued study drug or all available data at the time of the database snapshot for subjects those who were ongoing at the time of an interim analysis. The analysis will be based on values reported in conventional units. When values are below the limit of quantitation, they will be listed as such, and the closest imputed value will be used for the purpose of calculating summary statistics. For example, if “< 0.2” was recorded, a value of 0.1 will be used for the purpose of calculating summary statistics; if “< 0.1” was recorded, a value of 0.09 will be used for the purpose of calculating summary statistics.

A by-subject listing for laboratory test results will be provided by subject ID number and visit in chronological order for hematology, serum chemistry, and urinalysis separately. Values falling outside of the relevant reference range and/or having a severity grade of 1 or higher on the Gilead Grading Scale for Severity of Adverse Events and Laboratory Abnormalities will be flagged in the data listings, as appropriate.

No inferential statistics will be generated.

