7.2.2.1. Treatment-Emergent Laboratory Abnormalities

Treatment-emergent laboratory abnormalities are defined as values that increase at least 1 toxicity grade from baseline at any postbaseline time point, up to and including the date of last dose of study drug plus 30 days for subjects who permanently discontinued study drug, or all available data in the database snapshot for subjects who were still on treatment at the time of an interim analysis. If the relevant baseline laboratory value is missing, then any abnormality of at least Grade 1 will be considered treatment emergent.

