7.2.2.2. Summaries of Laboratory Abnormalities

Laboratory data that are categorical will be summarized using the number and percentage of subjects in the study with the given response at baseline and each scheduled postbaseline visit.

The following summaries (number and percentage of subjects) for treatment-emergent laboratory abnormalities will be provided by analyte and treatment group; subjects will be categorized according to the most severe postbaseline abnormality grade for a given analyte:

- Graded laboratory abnormalities
- Grade 3 or above laboratory abnormalities

For all summaries of laboratory abnormalities, the denominator is the number of subjects with nonmissing postbaseline values up to 30 days after last dose for the laboratory parameter of interest.

A by-subject listing of treatment-emergent Grade 3 or above laboratory abnormalities will be provided by subject ID number and visit in chronological order. This listing will include all test results that were collected throughout the study for the analyte of interest, with all applicable severity grades or abnormal flags displayed.

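### Appendix 3 has no lymphocyte grade at age 13 or under and the SAP makes ungraded values Grade 0, so the graded lymphocyte rows are 0% by rule in every 3 to <12-year column

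*SAP*

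**What the plan says.** Protocol 9.5.4 fixes the scale: "Graded laboratory abnormalities will be defined using the grading scheme in Grading of Laboratory Abnormalities provided in" Appendix 3. That appendix has a single lymphocyte row, headed "Absolute Lymphocyte Count HIV NEGATIVE ONLY Adult and Pediatric > 13 Years". Its cut-offs run from 650/mm3 (top of Grade 1) to below 350/mm3 (Grade 4). No row covers younger subjects.

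SAP 7.2.2 has no category for a value that cannot be graded. It states that "Grade 0 includes all values that do not meet the criteria for an abnormality of at least Grade 1".

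SAP 7.2.2.1 counts as treatment-emergent those "values that increase at least 1 toxicity grade from baseline at any postbaseline time point", up to 30 days after the last dose. SAP 7.2.2.2 tabulates these by analyte and treatment group, once for all grades and once for Grade 3 or above, and says that "the denominator is the number of subjects with nonmissing postbaseline values up to 30 days after last dose for the laboratory parameter of interest".

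SAP 1.2 plans "Approximately 50 children aged 3 to < 12 years" and a similar number of adolescents. Lymphocytes belong to the hematology panel (Protocol 6.6.1), which is drawn at every on-treatment visit.

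**The concern.** Each rule is ordinary taken alone. Together they turn the absence of a grading criterion into a finding of normality. A child aged 8 with a very low lymphocyte count is Grade 0 at baseline and Grade 0 afterwards, stays in the denominator, and adds nothing to the numerator. The table then shows no lymphopenia in the younger children because of how the scale was built, not because of how they responded to treatment.

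Safety and tolerability is the Treatment Phase primary objective, and Protocol 9.5.4 promises laboratory abnormality incidence by age group and overall. A reader comparing the age columns would see a lower rate in the younger group and could take it for a real difference. Nothing in the table would say that the row carries no information for that group. The by-subject listing of treatment-emergent Grade 3 or above abnormalities in SAP 7.2.2.2 has the same blind spot, since a lymphocyte count cannot trigger it at these ages.

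**Working it through.** The documents give no figure on this point, so there is none to reproduce. The check applies the stated rules.

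**1. Grade by age and count.** Appendix 3 cut-offs: Grade 1 is 600 to 650/mm3, Grade 2 is 500 to <600, Grade 3 is 350 to <500, Grade 4 is <350. Where no row exists, SAP 7.2.2 gives Grade 0.

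| Lymphocytes (/mm3) | Age 8 | Age 15 |
|---|---|---|
| 700 | 0 | 0 |
| 640 | 0 | 1 |
| 550 | 0 | 2 |
| 400 | 0 | 3 |
| 300 | 0 | 4 |
| 100 | 0 | 4 |

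The treatment-emergent numerator needs a rise of at least one grade. At age 8 none is possible. The rule for a missing baseline does not help, because it still needs a postbaseline value of at least Grade 1.

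**2. Can a child in the 3 to <12 group grow into the graded band?** SAP 3.6 uses age at first dose. Even with age at the sample, the oldest child is just under 12 at first dose, and the latest laboratory day is Week 24 (168) + 3 days of visit window + 30 days = 201 days. Age is then at most 12 + 201/365.25 = 12.55 years, which is below 13. So each 3 to <12-year column has numerator 0 for any data, over about 50 children in all.

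**3. The adolescent columns.** Assume ages uniform over 12 to <18 and 50 adolescents.
- Band starts just after 13.0: (13 − 12)/6 × 50 = 8.3, about 8 ungradable.
- Band starts at 14 (age in completed years above 13): (14 − 12)/6 × 50 = 16.7, about 17 ungradable.

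These subjects stay in the denominator with a forced zero. A rate r among gradable adolescents is therefore shown as about (41.7/50) r = 0.83 r in the first case, or (33.3/50) r = 0.67 r in the second.

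**4. What the forced zero could hide.** The documents give no lymphopenia rate, so take a range of assumed true rates p under some age-appropriate cut-off. Among 50 children the expected number is 50p, and the chance of at least one case is 1 − (1 − p)^50.

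| p | Expected cases | Chance of at least one | Graded table shows |
|---|---|---|---|
| 2% | 1 | 64% | 0 |
| 5% | 2.5 | 92% | 0 |
| 10% | 5 | 99.5% | 0 |
| 20% | 10 | >99.9% | 0 |

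**The case against.** The strongest reply is that lymphocyte evidence is not missing, and this stands. SAP 7.2.1 names lymphocytes among its 11 analytes. It gives the full set of descriptive statistics, minimum included, at baseline and each postbaseline window, with change from baseline and a median plot by treatment group. SAP 7.2 plans laboratory listings "for hematology, serum chemistry, and urinalysis separately" and flags values outside the reference range whether or not they carry a grade. In Appendix 3, WBC has no age limit and neutrophils are graded from 7 months, so other white-cell toxicity in young children is graded. The primary safety endpoint, an adverse event leading to permanent discontinuation, does not use laboratory grades.

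It can also be said that a programmer might footnote or suppress the row. That is possible, but the SAP does not call for it, and the stated rule gives zero.

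Three stronger readings are tempting but unsupported:
- A reader might treat zero of about 50 as setting an upper confidence limit on the lymphopenia rate. The plan computes no such limit. SAP 7.2 rules out inferential statistics for laboratory data, and the tables are by treatment group, which splits age by genotype.
- A reader might infer that every 12- and 13-year-old is ungradable. That depends on how the lower age bound is read, which the documents do not settle.
- A reader might add that thyroid function is never reported, since TSH is drawn on treatment but is absent from SAP 7.2.1 and has no laboratory grade in Appendix 3. SAP Section 3 says in general that collected data will be listed by subject, and Protocol 9.5.4 promises only selected laboratory summaries. No commitment is broken.

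**Conclusion.** The point holds for one analyte in the graded tables. Applied as written, Appendix 3 with SAP 7.2.2 and 7.2.2.2 gives 0% treatment-emergent lymphocyte abnormalities, at any grade and at Grade 3 or above, in every 3 to <12-year column. This needs no assumption about the data. The dilution among adolescents, about 8 or about 17 of 50, rests on uniform ages and on where the graded band starts.

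The consequence is a row that misleads in a safety table shown by age group. It is not a loss of safety data, and no primary safety or efficacy result changes. The numeric summaries and listings allow a careful reader to see low counts, but they do not reveal that the graded row was zero by construction.

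**What to change.** - SAP 7.2.2: state that an analyte with no grade for the subject's age is 'not gradable', and reserve Grade 0 for values that a criterion could have graded. State whether the lymphocyte band starts just after 13.0 years or at 14, and whether age at first dose or at sampling applies.
- SAP 7.2.2.2: for each analyte, use the number of gradable subjects with a postbaseline value as denominator, and print that n. The 3 to <12-year lymphocyte cells then show no gradable subjects instead of 0%.
- SAP 7.2.2.2: for subjects at ungraded ages, add the number and percentage with a postbaseline lymphocyte count below the laboratory's age-specific lower limit of normal. This assumes that the laboratory supplies age-specific limits; SAP 7.2 already relies on reference ranges for its flags.

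Optional, and not the correction of an error: a small TSH table with baseline, end of treatment, change, and shift against the reference range.

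The cost is a few sentences and table rows. No new data are needed and patient management does not change. If the SAP is already final, SAP Section 1 provides for recording the change in the clinical study report.

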7.2.2.1. Treatment-Emergent Laboratory Abnormalities

Treatment-emergent laboratory abnormalities are defined as values that increase at least 1 toxicity grade from baseline at any postbaseline time point, up to and including the date of last dose of study drug plus 30 days for subjects who permanently discontinued study drug, or all available data in the database snapshot for subjects who were still on treatment at the time of an interim analysis. If the relevant baseline laboratory value is missing, then any abnormality of at least Grade 1 will be considered treatment emergent.

7.2.2.2. Summaries of Laboratory Abnormalities

Laboratory data that are categorical will be summarized using the number and percentage of subjects in the study with the given response at baseline and each scheduled postbaseline visit.

The following summaries (number and percentage of subjects) for treatment-emergent laboratory abnormalities will be provided by analyte and treatment group; subjects will be categorized according to the most severe postbaseline abnormality grade for a given analyte:

- Graded laboratory abnormalities
- Grade 3 or above laboratory abnormalities

For all summaries of laboratory abnormalities, the denominator is the number of subjects with nonmissing postbaseline values up to 30 days after last dose for the laboratory parameter of interest.

A by-subject listing of treatment-emergent Grade 3 or above laboratory abnormalities will be provided by subject ID number and visit in chronological order. This listing will include all test results that were collected throughout the study for the analyte of interest, with all applicable severity grades or abnormal flags displayed.

7.2.2.3. On-Treatment Liver-Related Laboratory Events

The following liver-related laboratory events will be summarized using data from all the on-treatment postbaseline visits (up to 2 days after the last dose of any study drug):

- Aspartate aminotransferase (AST) or ALT > 3 × ULN and total bilirubin > 2 × ULN

- $ALT > 5 \times ULN$
- Total bilirubin $> 2 \times ULN$

For the composite criterion of AST or ALT and total bilirubin, AST or ALT and total bilirubin must meet the specified cut-offs at a given postbaseline time point; subjects will be counted once when the criterion is met. The denominator will be the number of subjects in the Safety Analysis Set with at least 1 postbaseline value of AST or ALT and total bilirubin at the same time point. For individual laboratory tests, subjects will be counted once based on the most severe postbaseline values when the criterion is met. The denominator will be the number of subjects in the Safety Analysis Set with at least 1 nonmissing postbaseline value for the test. A listing will be provided including ALT, AST, total bilirubin, direct bilirubin, alkaline phosphatase, HCV RNA (\log_{10}) and yes/no flag for subjects meeting at least 1 of the 3 criteria. All the available data for the subjects will be listed.

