### 7.2. Subject Stopping Rules for SOF

The Gilead Medical Monitor should be consulted prior to dose discontinuation of SOF unless the investigator believes that immediate action is warranted to ensure the continued safety of the subject.

Administration of SOF may be discontinued due to a clinical or laboratory event. There is no option for SOF dose reduction. If SOF is stopped for toxicity, it should not be restarted, RBV should be stopped and the subject should complete an Early Termination Visit.

Subjects who meet any of the following laboratory criteria must stop treatment with SOF and RBV:

- Elevation of ALT and/or AST >5x Day 1 or nadir, confirmed by immediate repeat testing
- Abnormal elevation of ALT >3x Day 1 and total bilirubin >2 x ULN, confirmed by immediate repeat testing
- Confirmed elevation of ALT >15 x ULN
- Any Grade 3 or greater rash associated with constitutional symptoms
- Any Grade 4 event or lab abnormality assessed as related to treatment with SOF

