#### 9.2.1.2. Safety Analysis Set

The primary analysis set for safety analyses will include subjects who were enrolled and have received at least one dose of study drug.

Treatment-emergent data will be analyzed and defined as data collected from the first dose of study drug through the date of last dose of study drug plus 30 days.

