## **9.5. Safety Analysis**

Safety analysis will be performed for PK Lead-in and overall study Treatment Phases respectively. Safety data will be summarized by age group, by GT, by overall and by age group and GT.

Safety will be evaluated by assessment of clinical laboratory tests, physical examinations, vital signs measurements, and by the documentation of AEs.

All safety data collected while on or after the first dose of study drug administration up to 30 days after the last dose of study drug will be summarized by cohort according to the study drug received.

Safety endpoints will be analyzed by the number and percent of subjects with events or abnormalities for categorical values or 8-number summary (n, mean, standard deviation, median, Q1, Q3, minimum, maximum) for continuous data.

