7.11. Changes From Protocol-Specified Safety Analyses

There are no deviations from the protocol-specified safety analyses.

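### The SAP counts liver-related laboratory events only to 2 days after the last dose; adding 30-day rows would catch a first crossing after stopping, at almost no cost

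*SAP*

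**What the plan says.** SAP 7.2.2.3 (On-Treatment Liver-Related Laboratory Events) defines three criteria: AST or ALT >3xULN with total bilirubin >2xULN at the same time point; ALT >5xULN; and total bilirubin >2xULN. They "will be summarized using data from all the on-treatment postbaseline visits (up to 2 days after the last dose of any study drug"). This matches SAP 3.7.2, which treats laboratory values up to last dose + 2 days as on-treatment. The section's denominators refer to postbaseline values and state no 2-day limit. The accompanying listing shows all available data for subjects meeting at least one criterion.

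Other provisions use 30 days:

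- Protocol 9.5: safety data "up to 30 days after the last dose of study drug will be summarized by cohort according to the study drug received".
- Protocol 9.2.1.2, on treatment-emergent data: "data collected from the first dose of study drug through the date of last dose of study drug plus 30 days".
- SAP 7.2, the parent section, on laboratory summaries: "will include data collected up to the last dose of study drug plus 30 days".
- SAP 7.2.2.1, on graded abnormalities: "up to and including the date of last dose of study drug plus 30 days for subjects who permanently discontinued study drug".

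Protocol 7.2 stops both drugs on several liver criteria. Two are relative to the child's own values: ALT and/or AST above 5 times Day 1 or nadir, and "Abnormal elevation of ALT >3x Day 1 and total bilirubin >2 x ULN, confirmed by immediate repeat testing". A third is absolute: ALT above 15xULN.

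**The concern.** Safety and tolerability is the primary objective of the Treatment Phase, and this is the only table that looks at transaminases and bilirubin together. Two of the stopping rules use the child's own Day 1 or nadir value, while the table uses multiples of ULN. A child with a low starting ALT can therefore be taken off drug before reaching any row of the table. If the liver tests go on rising after the last dose, the first qualifying value may fall after the 2-day cut. The row for the composite could then show one event too few, possibly none, although the qualifying sample lies inside the 30-day window used for the other laboratory and safety summaries.

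**Working it through.** The plan states no figure for this point, so the check compares windows and thresholds.

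**1. Days removed.** Protocol safety window 30 days, liver table 2 days: 30 − 2 = 28 post-dose days are not used.

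**2. Samples that exist in those days.** Protocol 6.5.1 draws chemistry at 4 weeks ±5 days: 28 − 5 = 23 to 28 + 5 = 33, so 11 possible days. None of the 11 is within 2 days of the last dose; 8 (days 23 to 30) are within 30 days; 3 (days 31 to 33) are outside both. Protocol 6.4.7 also draws chemistry at the Early Termination visit and gives no day limit after the last dose.

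**3. Can a child be stopped below the cut-offs?** Let b be Day 1 or nadir ALT in multiples of ULN. The relative rule, applied to ALT, is met above 5 × b.

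| b (xULN) | Rule met above (xULN) | Guarantees ALT >3xULN | Guarantees ALT >5xULN |
|---|---|---|---|
| 0.5 | 2.5 | no | no |
| 0.6 | 3.0 | yes | no |
| 0.8 | 4.0 | yes | no |
| 1.0 | 5.0 | yes | yes |

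Below b = 1.0 a child can be stopped without meeting the ALT >5xULN row. Below b = 0.6 the ALT part of the composite need not be met either.

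**4. The other stopping rules.** ALT above 15xULN already meets the ALT >5xULN row. The rule pairing ALT above 3 times Day 1 with bilirubin >2xULN already meets the bilirubin row. It need not meet the composite: with b = 0.5 the ALT part is reached at 3 × 0.5 = 1.5xULN.

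**5. What the 30-day graded tables show (Protocol Appendix 3, SAP 7.2.2.2).**

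- ALT >5xULN is the Grade 3 threshold, so a first crossing on days 3 to 30 is tabulated there, provided that baseline ALT was below Grade 3 (the tables count increases in grade).
- The bilirubin cut-off of 2xULN lies inside Grade 2 (>1.5 to 2.5xULN). A value above 2 and up to 2.5xULN cannot be told apart from one between 1.5 and 2xULN. Only values above 2.5xULN reach Grade 3.
- The composite does not appear, because graded summaries are made by analyte.

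**6. Worked case (assumed values).** Day 1 ALT is 0.5xULN. The drugs are stopped at a confirmed 2.6xULN (2.6 / 0.5 = 5.2 times Day 1) with normal bilirubin. On day 10 after the last dose, ALT is 4xULN and bilirubin 2.3xULN. The sample meets the composite and the bilirubin criterion, and neither is counted in SAP 7.2.2.3. In the graded tables it gives two separate Grade 2 entries (ALT >2.5 to 5xULN; bilirubin >1.5 to 2.5xULN), and it does not bring the child into the Grade 3 or above listing.

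**The case against.** The strongest reply is that the window is deliberate and labelled. The section title says On-Treatment, the cut agrees with SAP 3.7.2, and the protocol's laboratory section (9.5.4) asks only for values by visit and graded abnormalities to 30 days, both of which the SAP delivers. The liver table is an addition. This stands. A reader might infer that SAP 7.11, "There are no deviations from the protocol-specified safety analyses", is untrue. The documents do not support that, because the protocol specifies no liver-event table from which to deviate, and its 30-day sentence does not say that every table must run to 30 days.

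A second reply is that most children stopped for a liver signal are counted. This also stands. The value that prompts stopping is normally drawn on drug or within 2 days, and it counts if it meets a row. The reading that the cut generally removes children stopped for liver tests goes too far; the gap is limited to first crossings from day 3 onward.

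A third reply is that the event is visible elsewhere. This stands in part. ALT >5xULN has the Grade 3 table, an abnormality leading to discontinuation is recorded and tabulated as an adverse event, and all laboratory results are listed by subject. But the adverse event table does not apply the composite. The 4-week summary takes the record closest to day 28 when several fall in its window (SAP 3.7.3), so a day-10 peak may not appear in it. Finding the composite in raw listings requires a manual search.

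Finally, a reader might infer that the missed child is certainly absent from the liver listing. SAP 7.2.2.3 does not say whether the listing flag is limited to 2 days, so this is open.

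**Conclusion.** The point holds as a gap in coverage. It is not a contradiction of the protocol. A child stopped below the table's cut-offs who first meets a criterion on days 3 to 30 after the last dose is not counted in SAP 7.2.2.3. The loss matters most for the composite, which no other table reports, and next for bilirubin above 2 and up to 2.5xULN. For ALT >5xULN it is small because of the Grade 3 table.

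The size in children cannot be derived: the documents give no rate of liver events and no rate of late Early Termination visits. The figure of 28 of 30 days describes the calendar, not lost events. For scale, one uncounted child would be 1 of about 100 (1%), or 1 of about 50 (2%) in one age group. The argument assumes that some chemistry is drawn after day 2, which the 4-week visit ensures, and that liver tests can go on rising after the last dose. The remedy costs little, so it is worth making as a cheap improvement.

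**What to change.** In SAP 7.2.2.3:

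1. Keep the present rows, to last dose + 2 days, as the on-treatment count.
2. Add the same three criteria through last dose + 30 days.
3. Give each set of rows a denominator from its own window. At present a child whose only postbaseline values come after day 2 could enter the denominator but never the numerator.
4. Retitle the section to cover both windows, so that post-treatment values do not sit under an on-treatment heading.
5. State that the listing includes anyone meeting a criterion at any postbaseline time point. This settles the open question about the flag and also covers 4-week visits on days 31 to 33, which a 30-day row would miss.

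The cost is a few extra table rows and a second window in the program, with counts that may be slightly higher. No dose, visit or stopping rule is affected.
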